5.0 Stratification Factors

- None – Patients, along with their physicians, will determine which treatment arm is appropriate for their needs. The APBI technique to be utilized will be based on technical considerations, availability at the radiation oncology facility, insurance coverage considerations, and patient preference. In addition, after reduction mammoplasty patients will only be allowed if they undergo brachytherapy as the extensive manipulation of breast tissue at the time of surgery is felt to preclude reliable targeting with external beam photon or proton techniques.

6.0 Randomization/Registration Procedures

6.1 Randomization-none

6.2 Registration Procedures

Registration will entail confirming patient eligibility and signing the informed consent

6.21 Pretreatment tests/procedures, (see Section 4.0) will be completed within the guidelines specified on the assessment schedule.

6.22 All required baseline symptoms (see Section 10.0) must be documented and graded.

7.0 Clinical Protocol Treatment

7.1 Radiation Therapy

7.11 3D-CRT (photon) APBI

In situations where patients present to a radiation oncologist pre-operatively, if they meet study eligibility criteria they may be consented at that time for 3D-CRT APBI. After lumpectomy and axillary staging, at their postoperative visit in the radiation oncology department (generally 1-6 weeks following surgery) final pathology and eligibility will be confirmed. Consent may also be obtained for photon APBI at that time if it was not provided preoperatively or if the patient is consulting with the treating radiation oncologist for the first time. Patient must begin treatment \leq 10 weeks after their last surgery.

Radiation Details:

Localization, Simulation, Immobilization: Prior to the treatment planning CT scan patients must be immobilized in the supine position in an arm up or down position at the discretion of the treating radiation oncologist. The CT should start at or above the mandible and extend several cm below the inframammary fold (including the entire lung). Slice thickness should be 0.3 cm or less.

Treatment Planning/Delivery: Any combination of photon beams of energy 6MV or higher, with or without the addition of electrons of any energy, may be used provided that the dosimetric requirements of the planning target volume (PTV) and homogeneity are met. 3D-CRT should begin within 10 weeks of lumpectomy or re-excision of margins.

Image Guidance for IGRT: Cone-beam CT (CBCT) matched to soft tissue and or fiducial markers/clips placed at the time of lumpectomy or orthogonal kilovoltage (KV) images matched to fiducial markers/clips should be performed to ensure reproducibility of setup prior to initiation of each treatment. A manual registration can also be used to optimize the match prior to treatment.

Definition of Target Volumes: The radiation oncologist will identify and outline the tumor bed by noting contrasting areas of density and architectural distortion as well as the presence of clips or fiducials in the breast. Information from the surgical report, mammography, MRI and other available imaging should be taken into account when available. A margin of 1cm will then be added to the tumor bed in order to create the CTV. The CTV will be limited, however, to 5mm from the skin surface and by the posterior breast tissue extent (chest wall and pectoralis muscles are not to be included). The PTV is defined as a uniform 3mm expansion of the CTV to compensate for variability of set-up and any motion of the breast during treatment. The PTV is saved and is used to generate the beam aperture with an additional margin to take penumbra into account. Since a substantial part of the PTV often extends outside other patient (especially for superficial cavities), the PTV is then copied to a PTV_EVAL, which is edited. The PTV_EVAL is limited to exclude the part outside the ipsilateral breast and the first 5mm of tissue under the skin (in order to remove most of the buildup region for the DVH analysis). Bolus to improve anterior target coverage should not be used. It is preferred that the PTV does not exceed 25% of the breast volume. If it does, a delay of 1-3 weeks until the seroma decreases in size and another planning session is performed should be considered.

Dose Prescription to PTV: The prescribed radiotherapy dose will be 21.9 Gy in 7.3 daily fractions (total of 3 fractions). Radiotherapy should aim to be delivered on three consecutive work days. Per protocol $\geq 95\%$ of the target volume PTV should be covered by $\geq 95\%$ of the prescribed dose of 21.9Gy. Variation Acceptable $\geq 90\%$ of the target volume PTV should be covered by $\geq 90\%$ of the prescribed dose of 21.9Gy. The maximum dose should not exceed 115% of the prescribed dose.

Definition and Dose Limitations of Normal Tissues/Organs at Risk (OARs): The following normal tissue structures should be contoured for all patients by the physician: uninvolved normal breast, ipsilateral lung, contralateral lung, and heart.

Uninvolved ipsilateral normal breast: Includes the glandular breast tissue visualized by CT and the consensus definitions regarding “breast” from the RTOG breast atlas. The structure should be limited to 5mm from the skin surface to minimize inaccuracy of dose calculation at the skin surface. Per protocol $<35\%$ (variation acceptable $<50\%$) of the whole breast reference volume should receive $\geq 50\%$ of the prescribed dose and $<20\%$ (variation acceptable $<30\%$) of the whole breast reference volume should receive the prescribed dose.

Ipsilateral lung: May be contoured with auto-segmentation with manual verification. The volume receiving 20Gy should not exceed 2%. The volume receiving 10Gy should not exceed 7%. The volume receiving 5Gy should not exceed 15%.

Contralateral lung: The volume receiving 20Gy should be 0. The volume receiving 10Gy should be <1%. The volume receiving 5Gy should be <2%.

Heart: The heart should be contoured beginning just inferior to the level in which the pulmonary trunk branches into the left and right pulmonary arteries (PA) and extending to its most inferior extent near the diaphragm. Contouring along the pericardium itself, when visible, is appropriate. The esophagus, ascending and descending aorta, and inferior vena cava should be excluded. The volume of heart receiving 2.5Gy should be less than 40%.

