As the implanted device moves with the target, compensation for variability of treatment set-up and breathing motion is not needed; therefore planning target volume for evaluation (PTV_EVAL) = CTV = PTV. Therefore, within this protocol, only the PTV_EVAL will be referenced. The PTV_EVAL will be delineated as the breast tissue volume bounded by the uniform expansion of the applicator surface radius in all dimensions by 10 mm less the applicator volume and will be limited to 5 mm from the skin surface and by the posterior breast tissue extent (chest wall and pectoralis muscles are not to be included).

The volume of trapped air/fluid that displaces the target beyond 1 cm from the balloon/applicator surface should be considered by the physician. The area of trapped air/fluid will be contoured at each level and a total volume obtained. The percentage of the PTV_EVAL that the air displaces may be calculated but this will not be considered in the PTV prescription constraints outlined below. If brachytherapy APBI is attempted but aborted prior to initiation because target coverage or normal tissue constraints (see below) cannot be met, then an alternative APBI technique (3DCRT photon or proton APBI) may be attempted on this protocol.

Dose Prescription to PTV_Eval: The prescribed radiotherapy dose will be 21 Gy in 7 Gy daily fractions (total of 3 fractions). Radiotherapy should aim to be delivered on three consecutive work days. Per protocol $\geq 95\%$ of the target volume PTV should be covered by $\geq 95\%$ of the prescribed dose of 21 Gy. High dose rate treatment delivery is required. Variation Acceptable $\geq 90\%$ of the target volume PTV should be covered by $\geq 90\%$ of the prescribed dose of 21 Gy. The volume receiving 150% and 200% (V150% and V200%) of the prescribed dose or more should be $\leq 35\text{cc}$ and $\leq 10\text{cc}$, respectively. Variation Acceptable V150%

<50cc and V200% <15cc. The volume receiving 300% and 400% (V300% and V400%) of the prescribed dose should be reported.

Definition and Dose Limitations of Normal Tissues/Organs at Risk (OARs): The following normal tissue structures should be contoured for all patients: uninvolved normal breast, ipsilateral lung, contralateral lung, heart, skin, adjacent ribs.

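### Section 7.11 writes both photon coverage tiers on the PTV, although the same section creates PTV_EVAL as the volume for DVH analysis

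*Combined protocol and SAP*

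**What the plan says.** The photon target definitions in section 7.11 run in this order.

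- CTV: tumor bed plus 1 cm, then cropped. "The CTV will be limited, however, to 5mm from the skin surface and by the posterior breast tissue extent".
- PTV: "The PTV is defined as a uniform 3mm expansion of the CTV". Its stated job is aperture design: "The PTV is saved and is used to generate the beam aperture with an additional margin to take penumbra into account".
- PTV_EVAL: a copy of the PTV with two edits. "The PTV_EVAL is limited to exclude the part outside the ipsilateral breast", and it also drops "the first 5mm of tissue under the skin (in order to remove most of the buildup region for the DVH analysis".

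The next paragraph sets the prescription. The per-protocol tier asks that at least 95%, and the acceptable-variation tier that at least 90%, "of the target volume PTV should be covered by" at least 95% or 90%, respectively, of 21.9 Gy. PTV_EVAL is not mentioned again for photons.

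The other two techniques avoid the mismatch. Section 7.12 (brachytherapy) uses the same tier sentence but first declares "planning target volume for evaluation (PTV_EVAL) = CTV = PTV", so the label makes no difference there. Section 7.13 (protons) scores coverage on the CTV.

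**The concern.** Coverage at a given percentage of dose is read from a dose-volume histogram. Section 7.11 builds one volume for that purpose and then attaches the acceptance criteria to the other. As written, the volume made for DVH analysis has no criterion, and the aperture volume has both.

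The two volumes differ most where the cavity is shallow. There the literal PTV includes tissue between 2 and 5 mm under the skin, which the section itself treats as buildup region. The section also bars bolus as a means of improving anterior coverage. Two people checking the same plan could then assign it different tiers. A planner who took the sentence literally could also be drawn into raising dose in that layer, and section 7.11 sets no photon skin limit to hold it down.

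**Working it through.** The plan gives no figure for this point, so there is none to reproduce. The check asks how much of the PTV lies in the layer that PTV_EVAL removes, and what that does to a coverage reading.

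**Inputs from section 7.11:** CTV margin 10 mm; CTV stops 5 mm under the skin; PTV expansion 3 mm; PTV_EVAL starts 5 mm under the skin; tier limits 95%/95% and 90%/90%.

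**Assumptions (not in the documents):** flat skin; spherical bed of radius r whose top lies s mm under the skin; no posterior edit.

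**Depth of the layer.** The CTV reaches 5 mm depth at the shallowest, so the PTV reaches 5 - 3 = 2 mm. The disputed layer is 2-5 mm deep. An uncropped CTV reaches depth s - 10 and its PTV s - 13, so the layer vanishes once s - 13 is at least 5, that is from s = 18 mm.

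**One case by hand: r = 10 mm, s = 5 mm.** The CTV sphere has radius 20 mm with its centre 15 mm deep, cut at 5 mm. The cut face has radius √(20² - 10²) = 17.32 mm. The PTV surface follows a sphere of radius 23 mm below 3.5 mm depth, and the rounded 3 mm edge of the cut face above it. Volumes in units of π mm³:

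- Depth 3.5-5 mm: 529 × 1.5 - (11.5³ - 10³)/3 = 619.9
- Depth 2-3.5 mm: 300 × 1.5 + 2 × 17.32 × 2.764 + 5.625 = 551.4
- Layer: 619.9 + 551.4 = 1171.2 (from unrounded terms)
- Depth 5-38 mm: 529 × 33 - (23³ + 10³)/3 = 13068
- Share of PTV: 1171.2 / (1171.2 + 13068) = 8.2%

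**Share of the PTV shallower than 5 mm, by the same method:**

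| Bed depth s | r = 1.0 cm | r = 1.5 cm | r = 2.0 cm |
|---|---|---|---|
| 5 mm | 8.2% | 5.7% | 4.2% |
| 7 mm | 6.9% | 4.8% | 3.5% |
| 10 mm | 4.9% | 3.4% | 2.5% |
| 14 mm | 2.0% | 1.4% | 1.0% |
| 18 mm | 0% | 0% | 0% |

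A separate voxel calculation (0.5 mm grid) gives 8.1%, 5.6% and 4.1% at 5 mm.

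**Effect on the coverage reading.** Let f be the share above, e the coverage on PTV_EVAL, and u the part of the layer below 95% of dose. Then

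PTV coverage = e(1 - f) + f(1 - u).

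The extreme case is e = 100% and u = 100%. The PTV then reads 1 - f. For beds 5 mm deep that is 91.8% (r = 1.0 cm) and 94.3% (1.5 cm), both short of the per-protocol limit, and 95.8% (2.0 cm), which still meets it. So a plan that fully covers PTV_EVAL can lose the per-protocol tier, but need not.

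Setting PTV coverage to 95% gives the u at which the tier is lost: u = (e - 0.95)/f + (1 - e). For r = 1.0 cm at 5 mm depth this is 0 + 0.05 = 5% when e = 95%, and 0.05/0.0823 + 0 = 61% when e = 100%. The answer depends almost wholly on e, which the documents do not give, so no single threshold measures the problem.

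**The case against.** The best defence is that the intended reading is plain. The 5 mm crop is explained as being for DVH analysis, coverage is a DVH quantity, and PTV_EVAL has no other use, so a competent planner would score PTV_EVAL. That is probably right, and it keeps the point small. It does not remove it: the operative sentence says something else, and nothing in 7.11 reconciles the two.

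It is also fair that the paragraph heading, and the planning phrase "provided that the dosimetric requirements of the planning target volume (PTV) and homogeneity are met", are weak evidence. The proton section uses the same heading and phrase while scoring the CTV. The point rests on the two tier sentences alone.

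Underdosing of the layer is an assumption. Section 7.11 allows electrons of any energy to be added, so the dose at 2-5 mm cannot be presumed low in every plan.

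Little follows from the tier. The lower one is permitted by name, and the deviation scoring in Appendix II does not use these tiers.

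A reader might infer an effect on eligibility, since exclusion 3.43 turns on dosimetric criteria. That criterion points to a section 9.7 that is not in the available text, so no link to these tiers is shown. A reader might also take the 12 of 40 patients with less than 7 mm of tissue over the bed (section 1.2) as the share of photon plans affected. That figure comes from a cited brachytherapy series and does not describe the photon cohort.

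**Conclusion.** The photon coverage rule names a volume that section 7.11 itself reserves for another purpose, and it should be corrected. The wording mismatch is certain; its practical size is not. Under the model, the disputed layer is about 4-8% of the PTV for beds 5 mm deep (radius 2.0-1.0 cm), shrinking to nothing by 18 mm. The shares rest on flat skin, a spherical bed and no posterior edit. Any tier change also requires enough of the layer to be underdosed.

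A reader might go further and conclude that photon plans will often be misgraded, or that cosmesis or the primary analysis is affected. The documents do not support this. They give no dose in the layer, no photon cavity depths and no achieved PTV_EVAL coverage, so no frequency can be stated. The primary analysis (section 16.5) takes all eligible, consented patients who started treatment, whatever tier their plan received.

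Severity: minor.

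**What to change.** In section 7.11, under the dose prescription, replace the target volume named in both photon tier sentences with PTV_EVAL. Keep the PTV for aperture design. Aligning the paragraph heading and the planning phrase is optional tidying.

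The cost is a wording amendment. No dose or percentage changes and no new contour is needed, since PTV_EVAL is already required. Plans already made can have their coverage re-read on it.

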7.12 Catheter-based Brachytherapy APBI

Patients that elect to undergo brachytherapy APBI will consult with a radiation oncologist preoperatively. If they meet study eligibility criteria they may be consented at that time for brachytherapy APBI. At surgery (day 1), metal vascular or marking clips should not be used during the lumpectomy procedure. Immediately following lumpectomy and axillary staging and during the same procedure, if the patient still meets eligibility criteria the brachytherapy catheter device (SAVI, Mammosite, or Contura) will be placed. Care should be taken to direct suture knots and tails away from the cavity and whenever possible position tissue between the potential balloon surface and the tails. Prophylactic antibiotics should be initiated prior to device placement and continued until the device is completely removed from the patient. On day 2-4, the patient will present to the radiation oncology department for brachytherapy treatment planning, with the first treatment generally administered the following business day but possibly as early as day 2.

Radiation Details:

Localization, Simulation, Immobilization: Prior to the treatment planning CT scan patients must be immobilized in the supine position, generally with the arms up and resting comfortably in a reproducible position stabilized by an immobilization device. A treatment planning CT scan with the patient in a supine position and in a deep inspiratory breath hold will be performed within 4 days of the lumpectomy and device placement. The CT should start at or above the mandible and extend several cm below the inframammary fold (including the entire lung). Slice thickness should be 0.3 cm or less. Skin spacing, symmetry, and conformance of the applicator will be assessed at that time. An AP and lateral digitally reconstructed radiograph (DRR) should be constructed and the skin position of each catheter line should be marked on the skin for pre-treatment quality assurance. Finally, a photograph will be taken to document the orientation of the patient.

Treatment Planning/Delivery: Standard treatment planning guidelines for APBI will be employed and CT imaging is mandatory for treatment planning. Plans will be generated on Varian Eclipse Brachytherapy Treatment Planning software to produce the optimal conformal plan in accordance with volume definition and dose requirements. The treatment plan used for each patient will be based on analysis of the volumetric dose including dose-volume histogram (DVH) analyses of the PTV_EVAL and critical normal tissues. The treatment will be performed using the VariSource high dose rate (HDR) brachytherapy afterloader.

In general, brachytherapy should start between 1-5 days after device placement and treatment should be completed within 1 week of device placement. To confirm that the patient's setup is identical to the position of the initial planning CT, the applicator's position and integrity will be verified at the discretion of the treating physician with particular attention to applicator rotation and changes in soft tissue. This will be done by repeating the planning CT scan in the treatment position, assessing the position of the external catheter marker on the skin surface and by obtaining AP and Lateral planar radiographic images, CT scouts, or CT AP and Lateral views for verification of the balloon/strut size and shape. If a change in geometry is noted, this should be addressed prior to additional treatment and repeat planning should be considered at the discretion of the treating physician. The device should remain expanded throughout the treatment course.

Definition of Target Volumes: The following structures will be contoured: (a) the applicator surface (for example for the SAVI® device, the "device surface" is defined as a structure represented by a contour created by smooth contour connection of each strut), (b) planning target volume for evaluation (PTV_EVAL) – (see below), (c) trapped air and/or fluid, (d) skin (both a structure of 5mm of superficial tissue and a structure of the skin surface), (d) chest wall (including ribs), and (e) pectoralis major muscle. The target volumes and normal tissue structures should be outlined on all CT slices.

As the implanted device moves with the target, compensation for variability of treatment set-up and breathing motion is not needed; therefore planning target volume for evaluation (PTV_EVAL) = CTV = PTV. Therefore, within this protocol, only the PTV_EVAL will be referenced. The PTV_EVAL will be delineated as the breast tissue volume bounded by the uniform expansion of the applicator surface radius in all dimensions by 10 mm less the applicator volume and will be limited to 5 mm from the skin surface and by the posterior breast tissue extent (chest wall and pectoralis muscles are not to be included).

The volume of trapped air/fluid that displaces the target beyond 1 cm from the balloon/applicator surface should be considered by the physician. The area of trapped air/fluid will be contoured at each level and a total volume obtained. The percentage of the PTV_EVAL that the air displaces may be calculated but this will not be considered in the PTV prescription constraints outlined below. If brachytherapy APBI is attempted but aborted prior to initiation because target coverage or normal tissue constraints (see below) cannot be met, then an alternative APBI technique (3DCRT photon or proton APBI) may be attempted on this protocol.

Dose Prescription to PTV_Eval: The prescribed radiotherapy dose will be 21 Gy in 7 Gy daily fractions (total of 3 fractions). Radiotherapy should aim to be delivered on three consecutive work days. Per protocol $\geq 95\%$ of the target volume PTV should be covered by $\geq 95\%$ of the prescribed dose of 21 Gy. High dose rate treatment delivery is required. Variation Acceptable $\geq 90\%$ of the target volume PTV should be covered by $\geq 90\%$ of the prescribed dose of 21 Gy. The volume receiving 150% and 200% (V150% and V200%) of the prescribed dose or more should be $\leq 35\text{cc}$ and $\leq 10\text{cc}$, respectively. Variation Acceptable V150%

<50cc and V200% <15cc. The volume receiving 300% and 400% (V300% and V400%) of the prescribed dose should be reported.

Definition and Dose Limitations of Normal Tissues/Organs at Risk (OARs): The following normal tissue structures should be contoured for all patients: uninvolved normal breast, ipsilateral lung, contralateral lung, heart, skin, adjacent ribs.

Skin: The maximum dose at the skin surface should be reduced to as low as achievable while satisfying the other dose parameters but should not exceed 100% of prescription. If this constraint cannot be met than a different APBI technique can be considered on study. Ideally, the maximum dose of the first 5mm of superficial tissue from the body surface will also not exceed 125% of prescription and the maximum dose of the first 10mm of superficial tissue will not exceed 150% of prescription.

Chest wall (including ribs): Should be outlined on all CT slices when within 5mm of the PTV. The maximum dose and V0.1cc will be reduced to as low as achievable while satisfying all dose parameters but should not exceed 115% of the prescribed dose.

Uninvolved ipsilateral normal breast: Includes the glandular breast tissue visualized by CT and the consensus definitions regarding “breast” from the RTOG breast atlas. The structure should be limited to 5mm from the skin surface to minimize inaccuracy of dose calculation at the skin surface. Per protocol <35% (variation acceptable <50%) of the whole breast reference volume should receive $\geq 50\%$ of the prescribed dose and <20% (variation acceptable <30%) of the whole breast reference volume should receive the prescribed dose.

Ipsilateral lung: May be contoured with auto-segmentation with manual verification. The volume receiving 20Gy should not exceed 2%. The volume receiving 10Gy should not exceed 7%. The volume receiving 5Gy should not exceed 15%.

Heart: The heart should be contoured beginning just inferior to the level in which the pulmonary trunk branches into the left and right pulmonary arteries (PA) and extending to its most inferior extent near the diaphragm. Contouring along the pericardium itself, when visible, is appropriate. The esophagus, ascending and descending aorta, and inferior vena cava should be excluded. The volume of heart receiving 2.5 Gy should be less than 40%.

Applicator Removal: The applicator should be removed after completing the last fraction of treatment using standard technique. The applicator entrance/exit site should be dressed according to standard medical practice.

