1.4 Rationale for allowing 3 different APBI techniques

Prospectively conducted clinical trials have demonstrated the safety and efficacy of each of the APBI techniques that will be allowed on this study. On the recently closed NSABP B-39/RTOG 0413 protocol, A Randomized Phase III study of Conventional Whole Breast Irradiation Versus Partial Breast Irradiation for Women with Stage 0, I, or II Breast Cancer, APBI could be administered with brachytherapy or 3D-CRT at the physician's discretion, highlighting the equipoise that exists between the techniques and justifying pooling outcomes of patients treated with either technique on this study to assess the primary and secondary endpoints. Given the conformal and homogeneous dose distribution of protons as well as the favorable outcomes reported to date, proton APBI will also be allowed at centers where this modality is available. At least one of the three APBI techniques allowed in this study is available at all participating centers. Similar to NSABP-B-39/RTOG 0413, the APBI technique to be utilized will be at the physician's discretion and will be based on technical considerations, availability at the radiation oncology facility, insurance coverage considerations, and patient preference. In addition, after reduction mammoplasty patients will only be allowed if they undergo brachytherapy as the extensive manipulation of breast tissue at the time of surgery is felt to preclude reliable targeting with external beam photon or proton techniques.

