3.46 Extensive intraductal component

3.47 Active connective tissue disease

3.48 Reduction mammoplasty if 3DCRT or proton APBI are planned

3.49 Last surgery >10 weeks from enrollment

4.0 Test Schedule

Assessments, tests and procedures	Active Monitoring Phase				Observation
	Baseline ²	Radiation Treatment	Last day of radiation treatment (+/-2 days)	12 weeks (+/- 8 weeks) post-radiation	
History and Physical exam (including breast assessment/exam) ¹	X		X	X	X
Mammogram	X ¹¹				X ⁸
Consent	X				
Cosmetic and QOL Outcome Assessment (see section 11.3 and Appendix)	X		X	X	X
Digital Photograph	X ¹⁰		X	X	X
Histologic Assessment	X ³				
Radiation toxicity assessment (see section 10.4)	X		X	X	X
Serum pregnancy test	X ⁴				
Blood specimen ^{5,R}	X ¹²		X		
Clinically indicated treatment		X			

Surgical tumor specimen ^{6,R}	X ⁹				
----------------------------------------	----------------	--	--	--	--

1. A general clinical history & physical must be done \leq 8 weeks prior to registration. This should include assessment of ECOG performance status (see Appendix I).
2. Procedures done prior to radiation therapy.
3. Outside pathology must be reviewed at the treating institution.
4. For women of childbearing potential only
5. See section 14 for collection time and preparation of samples
6. See section 17 for collection time and preparation of samples
7. Patients that cannot come back to Mayo Rochester within the time constraints of the follow-up schedule; efforts to obtain outside records and send QOL's to be completed will occur however the specifics of the test schedule may not be captured. Observation will occur for a total of 5 years unless the patient goes off study.
8. As clinically indicated
9. Collect post-surgery
10. Ideally prior to surgery but can be done prior to radiation
11. Completed \leq 6 months prior to study entry
12. Radiation Oncology Registry and Biobank (IRB: 15-000136): Blood specimen is required to be collected prior to the start of radiation therapy.
- R. Research required testing

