7.13 Proton APBI

In situations where patients present to a radiation oncologist pre-operatively, if they meet study eligibility criteria they may be consented at that time for proton APBI. After lumpectomy and axillary staging, at their postoperative visit in the radiation oncology department (generally 1-6 weeks following surgery) final pathology and eligibility will be confirmed. Consent may also be obtained for

proton APBI at that time if it was not provided preoperatively or if the patient is consulting with the treating radiation oncologist for the first time. Patient must begin treatment \leq 10 weeks after their last surgery.

Radiation Details:

Localization, Simulation, Immobilization: Prior to the treatment planning CT scan patients must be immobilized in the supine position in an arm up or down position at the discretion of the treating radiation oncologist. Slice thickness should be 0.3 cm or less.

Treatment Planning/Delivery: Any combination of at least 2 proton beams may be used provided that the dosimetric requirements of the planning target volume (PTV) and homogeneity are met. Proton APBI should begin within 10 weeks of lumpectomy or re-excision of margins.

Image Guidance for IGRT: Orthogonal kilovoltage (KV) images matched to fiducial markers placed at the time of lumpectomy should be performed to ensure reproducibility of setup prior to initiation of each treatment.

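### The fallback from aborted brachytherapy to photon or proton APBI conflicts with the reduction-mammoplasty restriction and, on the proton route, with the image-guidance text

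*Combined protocol and SAP*

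**What the plan says.** The fallback appears twice in section 7.12. Under the target-volume text the trigger is: "If brachytherapy APBI is attempted but aborted prior to initiation because target coverage or normal tissue constraints (see below) cannot be met". The consequence is: "then an alternative APBI technique (3DCRT photon or proton APBI) may be attempted on this protocol". The skin constraint in the same section repeats the idea: "If this constraint cannot be met than a different APBI technique can be considered on study". Neither statement carries an exception or a cross-reference.

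Four other provisions bear on a woman who takes this route:

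- **Reduction mammoplasty.** Exclusion 3.48 reads: "Reduction mammoplasty if 3DCRT or proton APBI are planned". Sections 1.4 and 5.0 admit such women only if they undergo brachytherapy, because the surgery is "felt to preclude reliable targeting with external beam photon or proton techniques".
- **Lumpectomy for brachytherapy patients.** Section 7.12 instructs that "metal vascular or marking clips should not be used during the lumpectomy procedure". It mentions no other marker to be left in the breast.
- **Proton image guidance.** Section 7.13 states: "Orthogonal kilovoltage (KV) images matched to fiducial markers placed at the time of lumpectomy should be performed to ensure reproducibility of setup". This applies before each treatment, and no alternative is given.
- **Photon image guidance.** Section 7.11 allows cone-beam CT matched to soft tissue, to markers or clips, or to both, and alternatively kilovoltage images matched to markers or clips.

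**The concern.** The protocol foresaw the switch and wrote it down twice, but did not check it against the rules of the receiving techniques. Read literally, it permits external-beam treatment of women in whom the protocol itself says external-beam targeting is unreliable. It also permits a proton course whose daily set-up check cannot be carried out as written.

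This is more than untidy drafting. Section 1.3.2 relies on daily image guidance to justify the reduced planning volumes for photons and protons. The planning expansions are 3 mm for photons (7.11) and initially 5 mm for protons (7.13). Two sites could treat the same woman differently and both cite the protocol.

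There is a smaller statistical loose end. The suspension rules in 16.92 are evaluated by arm or modality, and the exploratory comparisons in 16.7 are made by technique. The plan does not say to which modality a switcher belongs.

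**Working it through.** The core of this point is textual and the plan gives no figure to reproduce. The check takes each route in turn.

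**Route 1: brachytherapy to photon, no reduction mammoplasty.** The woman has had a lumpectomy under 7.12, so she should have no metal clips. Section 7.11 accepts cone-beam CT matched to soft tissue. One of the permitted photon methods, kilovoltage matching to markers or clips, is probably lost to her, but another remains. Result: no conflict.

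**Route 2: brachytherapy to proton, no reduction mammoplasty.** Section 7.13 offers only kilovoltage matching to fiducials placed at lumpectomy. Under 7.12 the device is placed in the same procedure as the lumpectomy, and coverage is assessed afterwards on the planning CT. When the fallback is triggered, the operation is therefore over. A marker inserted later would not be one placed at lumpectomy. Result: the image-guidance step cannot be met as written by a woman managed under 7.12.

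**Route 3: brachytherapy to photon or proton after reduction mammoplasty.** At enrolment she passes 3.48, because brachytherapy is planned. Sections 1.4 and 5.0 go further: her place on study depends on undergoing brachytherapy. The fallback in 7.12 then permits either external-beam technique. Result: conflict on both routes.

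| Route | Reduction-mammoplasty rule | Image-guidance text |
|---|---|---|
| To photon, no reduction mammoplasty | not engaged | can be met (7.11) |
| To proton, no reduction mammoplasty | not engaged | cannot be met as written (7.13) |
| To photon, after reduction mammoplasty | conflict | can be met (7.11) |
| To proton, after reduction mammoplasty | conflict | cannot be met as written (7.13) |

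**How many women.** The protocol gives no fallback rate, no rate of reduction mammoplasty and no split of switchers between photon and proton. A ceiling can be shown only under an assumption. Suppose 5% to 15% of the brachytherapy cohort switch, and take the cohort size from 16.41 as 40 to 60:

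- low end: 0.05 × 40 = 2 switchers
- high end: 0.15 × 60 = 9 switchers

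These are all switchers. The women in conflict are the subset in the last three rows of the table, which could be none of them or all of them. Under this assumption the range is 0 to 9.

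**Modality assignment.** In 16.92, 3 events in the first 15 treated patients suspend accrual (3/15 = 20%), and later the trigger is a proportion of at least 20%. For these proportions to mean anything, a woman's event and the woman herself must be counted in the same modality. The plan has no rule that ensures this for a switcher.

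**The case against.** The best case for the current text is that the fallback is permissive and waives nothing. It says a switch may be attempted or can be considered, and it does not suspend eligibility. Exclusion 3.48 turns on what is planned, so it could be read as applying once an external-beam switch is proposed. Sections 1.4 and 5.0 are specific, and a careful site would let them prevail over a general permission. That reading is reasonable, but nothing in the protocol tells a site to adopt it.

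On markers, both sentences use *should*, and 7.12 bars metal clips, not every fiducial. Sections 7.11 and 7.13 list clips and fiducials as separate items. This stands: there is no literal ban on fiducials. What remains is that 7.12 makes no provision for one, so a woman managed under it would not be expected to have what 7.13 relies on.

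Three stronger readings are tempting and are not supported:

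- **That every switch breaches the protocol.** A woman without reduction mammoplasty who moves to photons with soft-tissue cone-beam CT breaches neither 7.11 nor 3.48.
- **That the event is common because section 1.2 cites 57% explantation.** That figure is for the single-lumen balloon device at skin distances below 7 mm, in a series treated with 10 fractions. The same account says none of the 12 patients with the strut device at that spacing needed explantation, and that device is allowed here. The figure shows that device failure is foreseeable; it does not estimate this trial's fallback rate.
- **That switchers would seriously distort the safety rules.** The fallback applies before any brachytherapy fraction, and 16.92 counts treated patients, so the technique that treated her is the natural home. Only events of grade 3 or higher that are at least possibly related count. The primary analysis pools techniques and the comparisons in 16.7 are exploratory. The gap is an unstated classification, not a demonstrated bias.

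**Conclusion.** Two conflicts stand in the current text. The fallback in 7.12 is at odds with 3.48, 1.4 and 5.0 for women after reduction mammoplasty, on both external-beam routes. It is also at odds with 7.13 for any woman who moves to protons after a lumpectomy managed under 7.12. The first is the clearer of the two, because the protocol itself gives the reason why these women should not reach external-beam treatment on study.

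The number affected is unknown and limited to those two groups. The conclusion assumes only that the sentences are applied as written; it does not depend on the assumed switch rate. No stated sample size, power or decision threshold changes. The point is worth acting on because it touches targeting and safety and is cheap to correct.

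**What to change.** Reconcile the two fallback sentences in 7.12 with 3.48, 1.4 and 5.0, and with the no-clips sentence in 7.12 and the image-guidance text in 7.13. Every woman offered the fallback should then be able to meet all the rules of the technique she receives. Which rule gives way, and how, is a clinical matter for the investigators.

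As a minor addition, state in 16.92 and 16.7 that each switcher belongs to one modality, the technique that delivered the dose, for both numerator and denominator. Counting device-related events under brachytherapy while the woman sits in another modality's denominator should be avoided, because it would distort the 20% rules. Flag switchers on the CRF so that the technique comparisons can be repeated without them.

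The cost is amendment wording and one CRF flag. The downside is that the fallback may be open to fewer women.
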